7.4.2 Reporting Adverse Events

Adverse Events that do not meet SAE criteria and that are not an AE of Interest will not be reported in the InForm database.

SAEs and AEs of Interest that occur from randomization through completion of the final study visit will be reported in the InForm database in the following manner:

- AEs of Interest that do not meet SAE criteria will be recorded on the AE eCRF.
- SAEs that require hospitalization will be reported on the HOSP eCRF noting the reason for the hospitalization. AEs of Interest that require hospitalization will be reported on the HOSP eCRF rather than the AE eCRF.
- Secondary SAEs that may occur while a subject is hospitalized due to a different reason will be reported on the AE eCRF.
- Deaths will be reported on the DEATH eCRF.
- If the subject was hospitalized for the event that led to death, the event will need to be reported both on the HOSP eCRF and the DEATH eCRF.

The Investigator will follow all SAEs and AEs of Interest until resolution, stabilization or the event is otherwise explained.

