5.1 Biomarker-guided Arm

In the Biomarker-guided arm, NT-proBNP values from the local clinical laboratory will be utilized by treating physicians for the purpose of achieving at NT-proBNP target of < 1000 pg/mL. The GUIDE-IT protocol will specify interventions to be considered to achieve the NT-proBNP target in the biomarker-guided arm, but specific treatment decisions will be at the discretion of the treating physician. The order of implementation will be based on clinical judgment, and more than one intervention can occur in a single encounter. Titration of neurohormonal antagonists will be emphasized over titration of diuretics except in the case of clinically apparent congestion or in the case of very high NT-proBNP levels, which usually indicate subclinical volume overload. Specific changes in therapy and the rationale for them (e.g., in response to clinical change or NT-proBNP levels) will be captured on the eCRF. Potential interventions to decrease NT-proBNP levels will include:

- Up-titrate or add Angiotensin Converting Enzyme (ACE)-inhibitor or ARB
- Up-titrate or add beta-blocker (if not clinically congested)
- Up-titrate or add hydralazine-nitrates in African-American patients
- Increase loop diuretic dosage (if clinically congested or NT-proBNP > 5000 pg/mL)
- Up-titrate or add spironolactone if tolerated by renal function and potassium
- Add oral thiazide diuretic
- Add digoxin
- Consider adding ARB to ACE-I (if not on spironolactone)
- Consider hydralazine-nitrates in non-African-American patients
- Intensified or repeated heart failure education regarding diet, sodium restriction, etc.
- Consider optimization of cardiac resynchronization therapy (if CRT device implanted)
- Reconsider potential indications for CRT (if not previously implanted)
- If in atrial fibrillation, maximize rate control or consider more aggressive attempts at normal sinus rhythm
- Consider exercise training or cardiac rehabilitation

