7.4 Safety

The main safety objectives in GUIDE-IT are to characterize the risk profiles of the two management strategies and to monitor for unanticipated risks to study participants. In this study, all medications and procedures commonly used or performed as a part of standard of care for the management of HF have well defined safety profiles. For this trial, reporting is primarily governed by the Common Rule (45 CFR Part 46, Subpart A), Investigational Device Exemptions (Part 812), as well as ICH Guidelines, IRBs and local regulations.

The investigator is responsible for monitoring the safety of subjects enrolled into the study at the study site. The investigator or qualified designee will enter the required initial and follow-up information regarding events into the appropriate module of the eCRF within InForm. Investigators are to report serious adverse events in accordance with their local IRB requirements. Investigators should follow usual clinical practices at their institution for reporting to regulatory authorities serious, unexpected events related to standard of care medications and devices.

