7.4.1 Definitions

An adverse event (AE) is any untoward medical occurrence in a patient or clinical investigational subject administered an investigational intervention and which does not necessarily have a causal relationship with this treatment. An AE can therefore be any unfavorable and unintended sign (including an abnormal laboratory finding), symptom, or disease temporally associated with the investigational intervention, whether or not considered related to the investigational intervention (ICH1996).

A serious adverse event (SAE) is any adverse event that may result in any of the following outcomes:

- Death
- Is life-threatening
- Results in persistent or significant disability/incapacity
- Is a congenital anomaly/birth defect
- Important medical event that may not result in death, be life-threatening, or require hospitalization may be considered a SAE when, based upon appropriate medical judgment, it may jeopardize the patient or subject and may require medical or surgical intervention to prevent one of the outcomes listed above

AEs of Interest for the GUIDE IT trial, which may or may not meet serious criteria, include any of the following:

- Symptomatic hypotension
- Symptomatic bradycardia
- Hyperkalemia (Potassium > 6.0 meq/dl or requiring change in therapy)
- Worsening renal function (increase in creatinine by 0.5 mg/dl from last visit or requiring change in therapy)

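### Non-serious low potassium and low sodium are not captured as adverse events, although the guided-arm options include more loop diuretic, added thiazide and added digoxin

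*Protocol*

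**What the plan says.** Protocol 7.4 sets the aim: "The main safety objectives in GUIDE-IT are to characterize the risk profiles of the two management strategies". Safety is also a listed secondary endpoint (7.2).

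Section 7.4.1 counts an abnormal laboratory result as an adverse event. It then lists four AEs of Interest, which are collected whether or not they are serious. Two are clinical: low blood pressure and slow heart rate, each only when it causes symptoms. The potassium item reads "Hyperkalemia (Potassium > 6.0 meq/dl or requiring change in therapy". The kidney item is worded as "Worsening renal function (increase in creatinine by 0.5 mg/dl from last visit or requiring change in therapy".

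Section 7.4.2 closes the list: "Adverse Events that do not meet SAE criteria and that are not an AE of Interest will not be reported in the InForm database".

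Among the guided-arm options, section 5.1 includes "Increase loop diuretic dosage (if clinically congested or NT-proBNP > 5000 pg/mL", "Add oral thiazide diuretic" and the addition of digoxin. The same section gives neurohormonal drugs priority over diuretics, except in patients with congestion or very high NT-proBNP. In usual care (5.2), diuretics are adjusted on clinical judgment and natriuretic peptides are not routinely measured.

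**The concern.** The four listed events suit up-titration of ACE-inhibitor or ARB, beta-blocker and spironolactone. They suit the diuretic options only in part. Low potassium and low sodium are familiar effects of intensified diuretic treatment, and potassium is relevant to the safety of digoxin. That link is general clinical knowledge; the protocol does not spell it out.

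The difficulty is the combination of a list that counts potassium in one direction and a rule that keeps non-serious events off the list out of the database. A guided-arm patient whose potassium falls after a thiazide is added, and whose treatment is changed as a result, produces no adverse event record unless the event is judged serious. A patient whose potassium rises enough to require a change in therapy does produce one.

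The stake is the completeness of the safety comparison. A risk profile that reports high potassium but not low potassium or sodium gives the DSMB and the final report only part of the electrolyte picture. A later SAP cannot restore adverse events that the sites were told not to enter.

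**Working it through.** The protocol states no rate, power or precision for AEs of Interest, so there is no figure to reproduce. The check sets the sections side by side.

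1. **Is low potassium or low sodium an adverse event here?** Yes. The definition in 7.4.1 includes abnormal laboratory findings.

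2. **Is either on the list?** No. Of 4 items, 1 concerns potassium (high only) and 0 concern sodium.

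3. **Does a change in therapy bring it in?** No. That criterion is attached only to hyperkalemia and worsening renal function.

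4. **What happens when it is non-serious and off the list?** Under 7.4.2 it is not reported in InForm.

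5. **Which harms of the three drug options are still captured?**
   - Loop diuretic and thiazide: hypotension and renal decline are listed.
   - Digoxin: bradycardia is listed.
   - All three: serious events are recorded, with hospitalizations on the HOSP form and deaths on the DEATH form (7.4.2).
   - Each option therefore has at least one plausible harm on the list. What is missing is non-serious low potassium and low sodium.

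6. **Could diuretic use differ by arm?** The protocol gives no size, but three points bear on it.
   - The NT-proBNP trigger for more loop diuretic in 5.1 is an alternative to clinical congestion. Usual care has no routine counterpart, because the peptide is not routinely measured there.
   - Section 2.4 describes a 220-patient trial of BNP-guided therapy in which up-titration, diuretics included, was significantly greater in the guided arm.
   - Against this, 5.1 favors neurohormonal drugs, and usual care also adjusts diuretics.

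7. **Are the blood results available?** Electrolytes are drawn locally in both arms at each follow-up visit (6.3.2, Appendix A) and at reassessments after a therapy change (6.3.3).
   - Scheduled follow-up draws over 12 months: 2 (weeks 2 and 6) + 4 (months 3, 6, 9, 12) = 6.
   - Over 24 months: 2 + 8 (months 3 to 24 in steps of 3) = 10.
   - With 550 patients per arm and no losses: 550 × 6 = 3,300 to 550 × 10 = 5,500 scheduled draws per arm. Deaths and withdrawals lower both figures.

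8. **Are those results certain to reach the database?** Not from this text. Section 9.2 mentions laboratory results and follow-up worksheets but does not itemize follow-up electrolyte fields. The DSMB report contents in 8.14 and 10.11 name SAEs and any requested analyses, not electrolyte values.

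**The case against.** A reader might infer that the safety comparison cannot see the harms of diuretic intensification and digoxin, or that low electrolytes are wholly invisible to the trial. The documents do not support either reading. Hypotension, renal decline and bradycardia are listed. Serious cases are recorded, and the important-medical-event clause in 7.4.1 could bring in a marked electrolyte disturbance on medical judgment. Reasons for changes in HF therapy go on the eCRF (5.1, 6.3.2), so some events may leave a trace there. The rule in 7.4.2 excludes adverse event reports, not laboratory values.

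It can also be said that the list matches the neurohormonal emphasis of 5.1, that both arms adjust diuretics, and that 7.4 regards the drugs as having well-defined safety profiles. Choosing which non-serious events to collect is the sponsor's decision, and a table of laboratory values may well be in the SAP.

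Most of this stands and sets the limits of the point. It does not remove it. Potassium and creatinine come from the same blood draws, yet the sponsor made high potassium and rising creatinine reportable events, each with a change-in-therapy criterion. Availability of the laboratory value was evidently not thought sufficient there. The exclusion of the low side is fixed in the protocol, and nothing in it commits to a by-arm comparison of low potassium or sodium.

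One further objection also stands. In an unblinded trial where 6.5 foresees more visits in the guided arm, investigator-reported low potassium could be found more often in that arm simply because it is looked for more often. This bears on which part of the fix should carry the comparison.

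**Conclusion.** The point holds in a limited form. Non-serious hypokalemia and hyponatremia, including cases that require a change in therapy, are not captured as adverse events. The guided-arm options nevertheless include drugs for which these events are relevant. It is a gap in event capture for two electrolyte disturbances, not a failure to observe the harms of those options in general. It does not touch the primary analysis.

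Its size in events cannot be given. The protocol states no incidence of low potassium or sodium and no expected difference in diuretic use, so any power or rate figure would rest on invented inputs. What can be counted is 0 of 4 listed events covering the low side, against 6 to 10 scheduled electrolyte draws per patient with complete follow-up.

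The conclusion assumes that 7.4.2 is applied as written. Whether a laboratory comparison can fill the gap depends on follow-up electrolyte values being entered in the eCRF, which this text leaves open.

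**What to change.** Two changes to the protocol, neither affecting treatment:

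1. In 7.4.1, add hypokalemia and hyponatremia to the AEs of Interest, with limits set by the sponsor.

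2. In 6.3.2 or 9.2, state that follow-up electrolyte values are entered in the eCRF. In 8.14, state that low potassium, high potassium and low sodium are tabulated by arm for the DSMB and in the final report. Use only the scheduled visits common to both arms (2 weeks, 6 weeks, then every 3 months). The chance of finding at least one low value rises with the number of draws, so including the extra reassessments would tilt the comparison against the arm that is seen more often.

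The scheduled-visit table should be the main comparison, because it does not depend on investigator reporting in an unblinded trial. The added AE terms supply what the table cannot: events between visits and events that required a change in therapy.

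The cost is two further AE terms, slightly more entry at sites and one extra safety table. No new blood draws are needed. Unequal reporting between arms remains possible for the AE terms and should be acknowledged where they are presented.

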8. STATISTICAL CONSIDERATIONS

8.1 Determination and Justification of Sample Size

Several design factors and research objectives have been considered in developing an appropriate sample size for the study. First, patient enrollment has been determined so there would be a sufficient number of endpoints to provide a high degree of confidence for testing the primary hypothesis. Second, the statistical power for secondary endpoints has been considered, including the EQOL endpoints. Finally, the sample size has been determined to provide a reasonable level of confidence for detecting clinically important differences in outcome between the two strategies—even if current projections of enrollment rates and hypothesized differences in clinical outcomes between the two arms prove to be optimistic.

Based on the anticipated patient population, we have projected a 1-year CV death and HF hospitalization rate of 40% for subjects randomized to the usual care arm. We estimate our patient population will be similar to that on the EVEREST study, a contemporary multicenter trial of patients with systolic HF randomized at the time of HF hospitalization and followed for a median of 10 months.⁴⁸ In EVEREST, the event rate for CV death or HF hospitalization at 10 months was 41%. Given that the meta-analysis of Felker et al. found an aggregate reduction of about 30% in all-cause mortality with biomarker-guided therapy, the impact of biomarker-guided therapy can conservatively be expected to reduce the primary composite endpoint (which we expect to be more sensitive to the effects of the biomarker-guided strategy than all-cause mortality) by 20% (from 40% to 32% at 1 year).

Based on the event rates for each arm discussed above, we have determined the sample size required to provide high power for detecting the postulated 20% relative risk reduction. As we recognize that the actual event rates and the outcome differences between the two testing strategies in GUIDE-IT may vary somewhat from these estimates, and we have determined the power of the study under several different combinations of enrollment rates, event rates and effect sizes. We have conducted the power analyses using simulation studies to mimic the key features of GUIDE-IT. As the primary treatment comparisons will be based on a time-to-event endpoint using the Cox proportional hazards model, we created 1,000 data

sets under each condition, and analyzed them using the Cox regression model to estimate the power under a variety of assumptions about the enrollment rates, event rates and effect sizes (Table 2).

	Table 2. Summary of the Power Simulations for the Primary Endpoint								
Control	Biomarker-	Relative	Enrollment	Estimated	Number	Minimum	Total Study		
Event	guided	Event Rate	Rate (per	Power (%)	of Primary	follow-up	Duration		
Rate*	Event	Reduction	month)		Endpoint	(months)	(month)**		
	Rate*				Events				
40%	32%	20%	35	89.4	566	12	52		
40%	34%	15%	35	67.1	579	12	52		
35%	28%	20%	35	84.6	506	12	52		
35%	29.75%	15%	35	57.7	518	12	52		
45%	36%	20%	35	93.8	623	12	52		
45%	38.25%	15%	35	76.3	637	12	52		
40%	32%	20%	35	91.2	605	24	64		
40%	34%	15%	35	69.6	618	24	64		
35%	28%	20%	35	86.8	542	24	64		
35%	29.75%	15%	35	58.9	555	24	64		
45%	36%	20%	35	95.8	662	24	64		
45%	38.25%	15%	35	77.2	677	24	64		
40%	32%	20%	26.25	89.7	573	12	62		
40%	34%	15%	26.25	67.3	586	12	62		
35%	28%	20%	26.25	85.1	513	12	62		
35%	29.75%	15%	26.25	57.8	525	12	62		
45%	36%	20%	26.25	94.0	630	12	62		
45%	38.25%	15%	26.25	76.2	644	12	62		

Table 2. Summary	of the Power Simulations for the Primary Endp	oint
	of the rower simulations for the rinning Endp	

*1-year event rate.

**Duration from study award date to last patient in the last study visit—the assumed yearly rate of loss to followup was 4% and the yearly non-CV death rate was 4%.

8.2 Projected Enrollment rate

We anticipate starting enrollment within 6 months from the study award date to finalize the protocol, complete DSMB review and approvals, and activate the sites. Given the complexities of site contracts, IRB approvals and regulatory requirements, we conservatively expect to activate 5 sites each month for enrollment. The recent NHLBI-funded HF-ACTION study enrolled a similar patient population, but required those patients to complete exercise training, which limited recruitment. The average enrollment for HF-ACTION in the U.S. was 0.84 patients per site per month. The 2-site STARBRITE study of biomarker-guided therapy enrolled 137 patients over a 28-month period for an average rate of 2.4 patients per site per month³². In the single-center PROTECT study of biomarker-guided therapy, a total of 151 patients were enrolled over a 2-year period for an average rate of 6.3 patients per site per month. ⁴⁹ For ASCEND HF, the U.S. enrollment rate varied between 1.5-2 patients per site per month. GUIDE-IT's enrollment will resemble a combination of these trials—patients will be identified at the time of acute HF, and, much like an outpatient HF study, they will be randomized soon after discharge. We believe that once a site is activated, an enrollment rate of 1 patient per site per month.

8.3 Projected Event Rates

In EVEREST, the event rate for CV death or HF hospitalization at 10 months was 41%. Based on a similar patient population, we have assumed a 1-year event rate with a 40% control arm, which we believe is a conservative estimate. Unlike EVEREST, GUIDE-IT will require elevated natriuretic peptide levels during the

index hospitalization, a powerful marker of increased risk, suggesting GUIDE-IT will have a higher event rate than EVEREST. Power simulations were conducted varying this rate from 35% to 45%. Event times were created using randomly generated exponential variables. The non-CV death and the loss-to-follow-up rates were generated as independent exponential random variables with 1-year event rates of 4% for each variable. In the simulations, the primary outcome variable was censored if the non-CV death or loss-tofollow-up occurred first. The non-CV death rate was based on unpublished data from EVEREST. Drop-in and drop-out rates were assumed to be distributed uniformly in 5% of subjects over the 2-year follow-up. At the time of drop-in or drop-out, the hazard rate was switched to the rate for the other treatment group.

8.4 Anticipated Effect Size

We planned the sample size to detect a relative reduction in the 1-year event rate of 0.20. The power simulations shown below also examine the power with 15% relative reductions. Simulations with relative event rate reductions greater than 25% typically resulted in power greater than 99%. Results are based on 1,000 simulated data sets in each scenario with a 2-sided Type I error rate of 0.05 (Table 2). The estimated power is based on the proportion of simulations using the Cox regression model Wald chi-square p-value < 0.05. It is expected that the final subject enrollment will be followed for 12 months resulting in follow-up times varying from 12 to 24 months. However, to illustrate the power increase of additional follow-up, we have examined scenarios with 24 months follow-up on all patients.

Based on our best estimates for event rates and enrollment with a 20% reduction in events from a 1-year rate of 40% in the control group to 32% in the biomarker-guided group, we anticipate having 89.4% power with the proposed sample size of 1,100 subjects. With the same event and enrollment rates, we would have a slight increase in power to 91.2% if every subject was followed for 24 months. If per site enrollment is lower than we project at 1 patient per site per month and is closer to 0.75 patients per site per month, Table 1 shows that we can still achieve our target number of primary outcome events by extending the study duration by 10 months. Alternatively, we will have the option of adding more sites in order to maintain total study enrollment at 35 patients per month.

Although GUIDE-IT has been powered for the primary endpoint of time-to-CV death or HF hospitalization, a key secondary endpoint is the time to all-cause mortality. The power for this endpoint was evaluated with simulations as described above. With an assumed 1-year all-cause mortality rate of 25% in the control group, we estimated the power at 86.0% and 96.3% to detect relative event rate reductions of 25% and 30%, respectively, which are consistent with the treatment effect seen in a recent meta-analysis of biomarker-guided therapy.

8.5 Power Calculations for Age Group by Treatment Interaction

Two prior studies (TIME-CHF and BATTLESCARRED) stratified randomization by age (> or < 75) and prespecified sub-group analysis based on age.^{31,33} Although these subgroups were small, the beneficial effects of biomarker guidance in both studies appeared to be primarily in patients < 75. Given that HF is primarily a disease of the elderly, whether there is a differential treatment effect based on age is of substantial clinical relevance and will be examined in GUIDE-IT. To determine the power to detect possible interactions by age, we have simulated data as described above. Additional parameters were added to define the proportion of the population above 75 years of age, and to define event rates that differ by age group. A binary variable was created to identify those patients in the biomarker-guided group and those 75 or more years of age. The results of the simulations are shown in Table 3. With a sample size of 1,100 patients, we have more than 99% power to detect large, qualitative interactions by age group. As expected, the power to detect quantitative interactions is not as great. If we assume 25% of patients are in the older age group, 40% vs. 30% 1-year event rates in the younger group, and 40% vs. 40% 1-year event rates in the older group, we will have 71.6% power to detect a statistically significant interaction at the 2sided 0.05 level.

In summary, our calculations suggest that a cohort of 1,100 patients will provide robust statistical power for detecting clinically relevant and realistic benefits of NT-proBNP-guided therapy for the primary and key secondary endpoints. Furthermore, this sample size estimate accounts for a combined 8% loss to follow-up or death due to non-CV causes and an allowance for 5% drop-in and drop-out.

Table 3. Power Simulations for the Interaction between Treatment and Age Groups								
Proportion of the	Treatment difference in	Treatment difference in	Estimated power to detect					
population greater than 75	the younger cohort	the older cohort	the interaction effect (%)					
years old	(control vs. biomarker-	(control vs. biomarker-						
	guided – 1 year rates)	guided – 1 year rates)						
20%	40% vs. 30%	40% vs. 50%	99.8					
25%	40% vs. 30%	40% vs. 50%	99.9					
33.3%	40% vs. 30%	40% vs. 50%	99.9					
20%	40% vs. 30%	40% vs. 42%	80.7					
25%	40% vs. 30%	40% vs. 42%	88.9					
33.3%	40% vs. 30%	40% vs. 42%	92.6					
20%	40% vs. 30%	40% vs. 40%	66.2					
25%	40% vs. 30%	40% vs. 40%	71.6					
33.3%	40% vs. 30%	40% vs. 40%	80.7					
20%	40% vs. 30%	40% vs. 38%	49.1					
25%	40% vs. 30%	40% vs. 38%	54.4					
33.3%	40% vs. 30%	40% vs. 38%	61.6					

Table 3. Power Simulations for the Interaction betwee	n Treatment and Age Groups
---	----------------------------

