6.2 Randomization

Subjects who fulfill all the inclusion criteria and none of the exclusion criteria will be randomized in a 1:1 fashion using the Simple Internal Randomization Engine (SIRE) system to either biomarker-guided therapy or usual care. The unit of randomization will be at the patient level rather than the site level. Treatment allocation will be conducted using a complete randomization scheme. At randomization, subjects will undergo a brief interval history and physical exam, cardiovascular (CV) medication history, local laboratory testing for renal function and electrolytes, assessment for adverse events, 6 minute walk test, QOL questionnaires, medical resource use and cost assessment, and core laboratory samples.

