8.8 Analysis for the Primary Hypothesis

The statistical comparison of the two randomized arms with respect to the primary endpoint will be a time-to-event analysis, and therefore will be based on the time from randomization to the first occurrence of CV death or HF hospitalization. The Cox proportional hazards regression model will be the primary tool to analyze and assess outcome differences between the two treatment arms. A hazard ratio and 95% confidence interval for summarizing the difference in outcomes between the two treatment arms will be computed using the Cox model. This comparison will constitute the primary statistical assessment of the effect of biomarker guidance versus usual care on overall clinical outcomes. The Cox model will include an indicator variable for treatment group and baseline adjustment variables for age, sex, NT-proBNP, diabetes mellitus and ejection fraction.

In order to select the best set of adjustment covariates, we reviewed prognostic models from other large datasets in chronic HF. We selected covariates based upon the importance of choosing variables with

minimal missing data and adjusted the primary analysis for the following baseline variables: age, sex, NT-proBNP, ejection fraction, and diabetes mellitus.

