8.11 Multiple Comparisons and Composite Endpoints

With the primary hypothesis and the various secondary endpoints, there is a multiplicity of analyses to be performed and an increased probability that at least one of the comparisons could be "significant" by chance. There are adjustments (e.g., based on the Bonferroni inequality) that can be used to preserve the overall type I error level by adjusting for the multiplicity of secondary endpoints by requiring small significance levels for every comparison. We will be conservative in the interpretation of these analyses, taking into account the degree of significance, and looking for consistency across endpoints. Also, we have pre-specified the primary and secondary outcome variables to help avoid over-interpretation and to reduce the problems inherent with multiple testing. A related issue is the interpretation of composite endpoints in clinical trials. To understand the importance of the components of the primary endpoint, we will estimate the treatment effect and frequency of each component (CV mortality and HF hospitalization) separately. Based on the prior biomarker-guided studies in HF, we have pre-specified age (\geq 75 or < 75 years of age) as a key subgroup of interest. The examination of this subgroup will include a formal test of interaction with the Cox regression model. Hazard ratio plots with point estimates and 95% confidence intervals will be used to examine the consistency of the treatment effect across subgroups.

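### Section 8.5 and Table 3 overstate the power of the age-by-treatment interaction test: the figures match a model with no age-group main effect, and the text example falls from 71.6% to about 44%

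*Protocol*

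**What the plan says.** Section 8.5 of the Protocol simulates the age interaction on the same basis as the primary endpoint, adding the share of patients over 75 and event rates by age group. The only model term it describes is this: "A binary variable was created to identify those patients in the biomarker-guided group and those 75 or more years of age". It mentions no term for age group itself.

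Two conclusions are drawn. For the extreme scenarios (40% v 50% in the older group): "With a sample size of 1,100 patients, we have more than 99% power to detect large, qualitative interactions by age group". For the example in the text ("If we assume 25% of patients are in the older age group", 40% v 30% younger, 40% v 40% older), at two-sided 0.05: "we will have 71.6% power to detect a statistically significant interaction". Table 3 gives 12 values, from 49.1% to 99.9%.

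Section 8.11 makes age 75 the key pre-specified subgroup: "The examination of this subgroup will include a formal test of interaction with the Cox regression model". Section 8.8 describes the primary model: "The Cox model will include an indicator variable for treatment group and baseline adjustment variables for age, sex, NT-proBNP, diabetes mellitus and ejection fraction". It does not say whether age enters as a continuous variable or as the 75-year split.

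**The concern.** An interaction test asks whether the treatment hazard ratio differs between older and younger patients. In a Cox model that takes three terms: treatment, age group and their product. If age group is left out, older and younger controls are forced to share one hazard. The product coefficient then compares older guided patients directly with younger guided patients. This has two consequences:

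- The test looks more precise than it is, because uncertainty in the control arm's age contrast drops out of the variance.
- Any prognostic effect of age is counted as interaction.

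Section 8.5 describes only the product variable, and its power values look high for 1,100 patients and about 570 events. At stake is how a reader weighs the result for the one key subgroup. The protocol presents the text example as having roughly 70% power, whereas a test with less than 50% power would miss that interaction more often than it found it.

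**Working it through.** **Inputs, all from the Protocol.** N = 1,100 (8.5); patients "will be randomized in a 1:1 fashion" (6.2); two-sided 0.05 (8.5); Cox Wald test, follow-up of 12 to 24 months, 35 patients per month (8.4); exponential event times, 4% yearly non-CV death, 4% yearly loss, 5% crossover uniform over 2 years with the hazard switching to that of the other arm (8.3); rates and age shares from Table 3.

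**Set-up check against Table 2** (1,000 runs each). 40% v 32% gives 565 events and 90.2% power (stated 566 and 89.4%). With 24 months for all it gives 605 events and 91.3% (stated 605 and 91.2%). The simulation therefore represents the protocol's design.

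**Closed form for the text example, without crossover.**

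- Yearly hazards: −ln(0.60) = 0.511 and −ln(0.70) = 0.357.
- Log hazard ratio, younger: ln(0.357/0.511) = −0.359. Older: 0. Difference: 0.359.
- Enrolment lasts 1,100/35 = 31.4 months, so (31.4 − 12)/31.4 = 62% of patients have the full 24 months and the rest are spread over 12 to 24.
- With censoring hazard −2 ln(0.96) = 0.082 per year, the event probability is about 0.562 at 40% and 0.442 at 30%.
- Expected events: control-young 412.5 × 0.562 = 232; guided-young 412.5 × 0.442 = 182; control-old and guided-old 137.5 × 0.562 = 77 each.

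| Model | Standard error | 0.359/SE | Power |
|---|---|---|---|
| No age-group term | √(1/182 + 1/77) = 0.136 | 2.64 | Φ(2.64 − 1.96) ≈ 75% |
| With age-group term | √(1/232 + 1/182 + 1/77 + 1/77) = 0.189 | 1.90 | Φ(1.90 − 1.96) ≈ 48% |

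Crossover pulls both down.

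**Simulation with 5% crossover, 6,000 data sets per row.** Power in %; rates are control v guided in the older group (younger group always 40 v 30).

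| Older rates | Share 75+ | Stated | No age-group term | With age-group term | Stated minus last |
|---|---|---|---|---|---|
| 40 v 50 | 20% | 99.8 | 99.5 | 89.9 | 9.9 |
| | 25% | 99.9 | 99.9 | 94.0 | 5.9 |
| | 33.3% | 99.9 | 100.0 | 96.2 | 3.7 |
| 40 v 42 | 20% | 80.7 | 80.8 | 52.6 | 28.1 |
| | 25% | 88.9 | 86.6 | 58.5 | 30.4 |
| | 33.3% | 92.6 | 90.8 | 64.2 | 28.4 |
| 40 v 40 | 20% | 66.2 | 66.5 | 39.2 | 27.0 |
| | 25% | 71.6 | 72.4 | 43.7 | 27.9 |
| | 33.3% | 80.7 | 79.1 | 50.8 | 29.9 |
| 40 v 38 | 20% | 49.1 | 48.4 | 28.3 | 20.8 |
| | 25% | 54.4 | 53.6 | 31.3 | 23.1 |
| | 33.3% | 61.6 | 60.7 | 35.7 | 25.9 |

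Without the age-group term, 11 of 12 rows agree within 2 points. The other differs by 2.3, about twice the standard error of that difference: √(0.889 × 0.111/1,000 + 0.866 × 0.134/6,000) = 1.1 points. With the age-group term, no row agrees within 2 points.

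**Could another setting explain 71.6% with the age-group term in?** None tried does: 24 months for all gives 47.2%, one-sided 0.05 gives 56.1%, and no 24-month cap with no crossover gives 52.0%.

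**The case against.** The strongest reply is that the printed numbers are not miscalculated. Every row of Table 3 sets the control rate at 40% in both age groups. In that world the product-only model is correctly specified and its power is about what the table says. That stands: the fault is the unstated condition that age has no prognostic effect, which a formal interaction test should not rely on. It is also true that the protocol does not print the fitted model, so its form is inferred.

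Three stronger readings are tempting, and the document does not support them.

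- *The trial will declare false interactions.* With no treatment effect and an assumed 45% or 50% 1-year rate in older patients, the product-only test rejects 24% or 69% of the time, against about 5% with the age-group term. But those rates are assumptions, and nothing says the analysis will use that model. Section 8.11 promises a formal interaction test and Section 8.8 already adjusts for age. If age enters only as a continuous covariate, power in the text example is about 59% under an assumed normal age distribution, still below 71.6%.
- *A non-significant interaction will be presented as proof of consistency.* The protocol does not say so. Section 8.5 concedes lower power for quantitative interactions, and Section 8.11 plans cautious interpretation and hazard-ratio plots with confidence intervals.
- *The trial is undersized.* Section 8.1 does not base the sample size on the age interaction.

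**Conclusion.** The point holds as a correction to stated power figures. The 71.6%, the claim of more than 99% and the rest of Table 3 are not the power of an interaction test that allows age its own effect. On the protocol's inputs that power is about 44% in the text example (47% to 48% if crossover is ignored), about 90% to 96% in the 40 v 50 rows, and about 28% to 64% in the others. This rests on the design inputs of Sections 8.3 to 8.5, on equal control rates in both age groups as Table 3 assumes, and on a model with treatment, age group and their product. That the age-group term was omitted is inferred from the single variable described and the 12-row match. The shortfall against the formal test does not depend on that inference.

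**What to change.** 1. Re-run Table 3 with treatment, age group (75 or older v younger) and their product in the Cox model, keeping the 5% crossover, and state the fitted model in Section 8.5.
2. Restate the text example as about 44% instead of 71.6%, and the large qualitative interactions as about 90% to 96% instead of more than 99%. The sponsor's re-run should supply the final values; the 43.7% here has a simulation standard error of √(0.437 × 0.563/6,000) = 0.6 points.
3. Have the interaction test in Section 8.11 use the same three-term model, so that the stated power and the planned test refer to the same thing and an age effect on prognosis cannot be read as interaction. If the statistical analysis plan already specifies this, a cross-reference is enough.

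The cost is one repeat of an existing simulation and a few sentences. The only downside is a less favourable stated power; no patients, visits or primary analyses change.
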